4. STUDY DESIGN

4.1 DESCRIPTION OF THE STUDY DESIGN

This study is a multicenter, randomized, double-blind, placebo-controlled, parallel group study of a single dose of SM04690 injected into the target knee joint of moderately to severely symptomatic OA subjects at Day 1.

Approximately 726 subjects will be enrolled and randomized at a ratio of 1:1 (0.07 mg active per 2 mL injection: 2 mL Placebo). Subjects will participate in a 7- to 11-day screening period followed by a single injection and a 28-week evaluation period. Clinic visits will be scheduled at the Screening Visit, Day 1, and Weeks 4, 12, 24, and 28 (EOS)/ET. Phone visits will be scheduled at Weeks 8, 16, and 20. Specific timing of protocol procedures is described in the Schedule of Events Table ([Section 7.3.7](#)). Specific timing of electronic diary and questionnaire completion is described in the Schedule of Electronic Diary and Questionnaire Completion Table ([Section 7.3.8](#)).

This study will be conducted at approximately 100 investigational centers.

A Widespread Pain Index and Symptom Severity (WPI&SS) assessment will be administered at the Screening Visit and Day 1.

Subjects will be required to complete an electronic diary for the following ([Section 7.3.8](#)):

- Daily pain NRS from the Screening Visit through Week 28 (EOS)
- WOMAC at baseline and Weeks 4, 12, 24, and 28 (EOS)
- Patient Global Assessment at baseline and Weeks 4, 12, 24, and 28 (EOS)

In addition, general medical evaluations including physical examination, knee examination, and recording of vital signs will be performed at the Screening Visit, Day 1, and Weeks 4, 12, 24, and 28 (EOS)/ET. Height will be measured at the Screening Visit and weight will be measured at the Screening Visit and Weeks 28 (EOS)/ET. Clinical laboratory evaluations will be performed at the Screening Visit and Weeks 4, 12, 24, and 28 (EOS)/ET. Investigator assessment of NSAID/acetaminophen usage will be performed at all in-person and phone visits starting at Day 1.

Recording of signs and symptoms of study medication intolerance and AE reporting will start following the injection of the study medication and continue at all subsequent in-person and phone visits until the subject completes Week 28 (EOS)/ET. All AEs, whether volunteered, elicited, or noted during examination, will be recorded throughout the study.

4.2 SCIENTIFIC RATIONALE FOR STUDY DESIGN

This phase 3 study, SM04690-OA-10, is a multicenter, randomized, double-blind, placebo-controlled, parallel group study of a single concentration of 0.07 mg SM04690 per 2 mL injection injected into the target knee joint of moderately to severely symptomatic OA subjects at Day 1. The placebo to be used in this study is a vehicle-concurrent control. The vehicle-only injection contains all components of the SM04690 injectable suspension with the exception of the active ingredient. Vehicle is considered the appropriate control in this study as it allows for evaluation of the efficacy, safety, and tolerability of the SM04690 molecule alone through comparison of the active and vehicle arms.

4.3 JUSTIFICATION FOR DOSE

The dose of 0.07 mg SM04690 was selected for this study based on evidence available from nonclinical studies and 3 completed clinical studies (SM04690-01, SM04690-OA-02, and SM04690-OA-04). Administration of the 0.07 mg dose resulted in the most consistently positive responses compared to control when the outcome measures of Pain NRS, WOMAC Function, and medial joint space width (mJSW) were assessed.

4.4 END OF STUDY DEFINITION

A participant is considered to have completed the study if he or she has completed all phases of the study including the last visit shown in the Schedule of Events Table ([Section 7.3.7](#)).

5. STUDY POPULATION

Eligibility of subjects will be determined by the following inclusion and exclusion criteria. Subjects should meet all the inclusion criteria and none of the exclusion criteria.

5.1 PARTICIPANT INCLUSION CRITERIA

In order to be eligible for the study, subjects must fulfill all of the following criteria:

1. Males and females between 40 and 80 years of age, inclusive, in general good health apart from their knee OA
2. Ambulatory (single assistive devices such as canes allowed if needed less than 50% of the time, subjects requiring a walker are excluded)
3. Diagnosis of femorotibial OA in the target knee by standard American College of Rheumatology (ACR) criteria at the Screening Visit (clinical AND radiographic criteria) ([Appendix 1](#)); OA of the knee is not to be secondary to any rheumatologic conditions (e.g., rheumatoid arthritis).
4. Radiographic disease Stage 2 or 3 in target knee within 24 weeks of the Screening Visit according to the Kellgren-Lawrence (KL) grading of knee OA as assessed by independent central readers
5. Pain compatible with OA of the knee(s) for at least 26 weeks prior to the Screening Visit
6. Primary source of pain throughout the body is due to OA in the target knee
7. Body mass index (BMI) $\leq 35 \text{ kg/m}^2$ at the Screening Visit
8. Widespread Pain Index (WPI) score of ≤ 4 and a Symptom Severity Question 2 (SSQ2) score of ≤ 2 at the Screening Visit and Day 1
9. Pain NRS scores recorded for the target knee on at least 4 out of the 7 days immediately preceding Day 1
10. Pain NRS scores recorded for the non-target knee on at least 4 out of the 7 days immediately preceding Day 1
11. Daily OA knee pain diary average NRS intensity score ≥ 4 and ≤ 8 in the target knee on the 11-point (0–10) NRS scale for the 7 days immediately preceding Day 1
12. Daily OA knee pain diary average NRS intensity score < 4 in the nontarget knee on the 11-point (0–10) NRS scale for the 7 days immediately preceding Day 1

13. WOMAC Function of 68–136 (out of 170) for the target knee at baseline regardless of if the subject is on symptomatic oral treatment
14. Willingness to use an electronic diary daily in the evening for the screening period and 28-week study duration
15. Negative drug test for amphetamine, buprenorphine, cocaine, methadone, opiates, phencyclidine (PCP), propoxyphene, barbiturates, benzodiazepine, methaqualone, and tricyclic antidepressants, unless any of these drugs are allowed per protocol and prescribed by a physician to treat a specific condition
16. Subjects with depression or anxiety must be clinically stable for at least 12 weeks prior to the Screening Visit and, if on treatment for depression or anxiety, be on at least 12 weeks of stable therapy
17. Full understanding of the requirements of the study and willingness to comply with all study visits and assessments
18. Subjects must have read and understood the informed consent form (ICF), and must have signed and dated it prior to any study-related procedure being performed

5.2 PARTICIPANT EXCLUSION CRITERIA

Any potential subject who meets one or more of the following criteria will not be included in this study:

1. Pregnant women, breastfeeding women, and women who are not post-menopausal (defined as 12 months with no menses without an alternative medical cause) or permanently surgically sterile (includes hysterectomy, bilateral salpingectomy, and bilateral oophorectomy) who have a positive or indeterminate pregnancy test result at the Screening Visit or Day 1
2. Women who are not post-menopausal or permanently surgically sterile who are sexually active, and who are not willing to use birth control (as outlined in [Section 5.3.1](#)) during the study period
3. Men who are sexually active and of reproductive potential, who have partners who are capable of becoming pregnant, and who are not willing to use birth control as outlined in [Section 5.3.1](#) during the study period
4. Significant malalignment of anatomical axis (medial angle formed by the femur and tibia) of the target knee (varus > 10°, valgus > 10°) by radiograph within 24 weeks of the Screening Visit as assessed by independent central readers
5. Partial or complete joint replacement in either knee
6. Currently requires use of a lower extremity prosthesis, and/or a structural knee brace (i.e., a knee brace that contains hardware)
7. Any surgery (e.g., arthroscopy) in either knee within 26 weeks prior to Day 1
8. Intra-articular (IA) injection into the target knee with a therapeutic aim including, but not limited to, hyaluronic acid, platelet-rich plasma (PRP), and stem cell therapies within 26 weeks prior to Day 1 or IA glucocorticoids within 12 weeks prior to Day 1
9. Effusion of the target knee clinically requiring aspiration within 12 weeks prior to Day 1
10. Use of electrotherapy (refer to [Appendix 2](#)), acupuncture, formalized physical therapy

(i.e., prescribed by a medical professional), therapeutic ultrasound, and/or chiropractic treatments for knee OA within 4 weeks prior to Day 1

11. Previous treatment with SM04690
12. Subjects who have previously failed screening on this protocol and fail to meet rescreening criteria (see [Section 5.4.2](#))
13. Participation in a clinical research trial that included the receipt of an investigational product (IP) or any experimental therapeutic procedure within 26 weeks prior to the Screening Visit, or planned participation in any such trial
14. Treatment with systemic (oral, intramuscular, or intravenous) glucocorticoids \geq 10 mg prednisone or the equivalent per day within 4 weeks prior to Day 1; or subjects on $<$ 10 mg prednisone or the equivalent per day who have not maintained a stable regimen for at least 2 weeks prior to Day 1 in the opinion of the Investigator
15. Use of centrally acting analgesics (refer to [Appendix 2](#)) within 12 weeks prior to Day 1
16. Use of anticonvulsants (refer to [Appendix 2](#)) within 12 weeks prior to Day 1
17. Subjects requiring the use of opioids $>$ 1x per week within 12 weeks prior to Day 1
18. Topical local anesthetic agents (gels, creams, or patches such as the Lidoderm patch) used for the treatment of knee OA within 7 days of Day 1
19. Planned surgery scheduled during the study period, not including non-surgical invasive procedures conducted for a diagnostic or therapeutic purpose scheduled during the study period (refer to [Section 7.6](#)).
20. History of malignancy within the last 5 years, not including subjects with prior history of adequately treated in situ cervical cancer or basal or squamous cell skin cancer
21. Clinically significant abnormal screening hematology values, blood chemistry values, or urinalysis values as determined by the Investigator
22. Any condition that, in the opinion of the Investigator, constitutes a risk or contraindication for participation in the study or that could interfere with the study objectives, conduct, or evaluation
23. Other conditions that, in the opinion of the Investigator, could affect study endpoint assessments of either knee, including, but not limited to, peripheral neuropathy (e.g., diabetic neuropathy), symptomatic hip osteoarthritis, symptomatic degenerative disc disease, and patellofemoral syndrome
24. Comorbid conditions that could affect study endpoint assessments of the target knee, including, but not limited to, rheumatoid arthritis, psoriatic arthritis, systemic lupus erythematosus, gout or pseudogout, and fibromyalgia
25. History of mania, bipolar disorder, psychotic disorder, schizophrenia, or schizoaffective disorder
26. Any known active infections, including urinary tract infection, upper respiratory tract infection, sinusitis, suspicion of IA infection, hepatitis B or hepatitis C infection, and/or infections that may compromise the immune system such as human immunodeficiency virus (HIV) at Day 1
27. Any chronic condition that has not been well controlled or subjects with a chronic condition who have not maintained a stable therapeutic regimen of a prescription therapy

in the opinion of the Investigator

28. Hemoglobin A1c (HbA1c) > 9 at the Screening Visit
29. If using NSAIDs and/or acetaminophen, subjects who have not maintained a stable regimen in the opinion of the Investigator for at least 4 weeks prior to Day 1
30. Any contraindications for an IA injection in the target knee in the opinion of the Investigator
31. Subjects who have a current or pending disability claim, workers' compensation, or litigation(s) that may compromise response to treatment
32. Subjects who are immediate family members (spouse, parent, child, or sibling; biological or legally adopted) of personnel directly affiliated with the study at any investigative site, or are directly affiliated with the study at any investigative site
33. Subjects employed by Samumed, LLC, or any of its affiliates or development partners (that is, an employee, temporary contract worker, or designee) responsible for the conduct of the study, or who are immediate family members (spouse, parent, child, or sibling; biological or legally adopted) of said employees responsible for the conduct of the study

5.3 LIFESTYLE GUIDELINES

5.3.1 CONTRACEPTION

WOMEN OF CHILDBEARING POTENTIAL

Women of childbearing potential (WOCBP) refers to women who are not post-menopausal (defined as 12 months with no menses without an alternative medical cause) or permanently surgically sterile (includes hysterectomy, bilateral salpingectomy, and bilateral oophorectomy).

From the Screening Visit until Week 28 (EOS), sexually active WOCBP must agree to use an acceptable form of contraception. Acceptable forms of contraception are:

1. Intrauterine device (IUD)
2. Implantable rod
3. Established hormonal contraceptive methods in combination with a barrier method. This includes injectable, oral, patch, and vaginal ring hormonal contraception. Females who are using hormonal contraceptives must have had consistent use of the same hormonal contraceptive product for at least 4 weeks. Barrier methods include male or female condom, diaphragm with spermicide, sponge with spermicide, or cervical cap with spermicide.
4. Bilateral tubal ligation/occlusion/division
5. Male partner who had a vasectomy provided that the partner is the sole sexual partner of the WOCBP, and that the vasectomized partner has received medical assessment of the success of the surgical procedure or had the vasectomy for at least 6 months

Sexually active WOCBP who withdraw from the study after receiving study medication should remain on an acceptable form of contraception for 28 weeks after Day 1.

MEN

For men who are sexually active with a female partner of childbearing potential, both partners must agree to use an acceptable form of contraception, as outlined below, from the Screening Visit until Week 28 (EOS):

- A condom and one additional acceptable form of birth control:
 - a. IUD
 - b. Implantable rod
 - c. Established hormonal contraceptive methods. This includes injectable, oral, patch, and vaginal ring hormonal contraception. Females who are using hormonal contraceptives must have had consistent use of the same hormonal contraceptive product for at least 4 weeks
 - d. Bilateral tubal ligation/occlusion/division
 - e. Vasectomy in the male partner for at least 6 months or demonstrated success of the surgical procedure

Men who are sexually active with a female partner of childbearing potential who withdraw from the study after receiving study medication should continue to use an acceptable form of contraception with their partners for 28 weeks after Day 1.

5.4 SCREEN FAILURES

5.4.1 SCREEN FAILURES

Screen failures are defined as participants who consent to participate in the clinical trial but are not subsequently randomized or entered in the study.

5.4.2 SUBJECT RESCREENING

Subjects are allowed to be rescreened once for this protocol and, if the subject is affected by an amendment(s) that changes the inclusion/exclusion criteria, they are additionally allowed to rescreen. Rescreens are limited to subjects who did not meet inclusion/exclusion criteria due to a transient reason or if the inclusion/exclusion criteria have changed. Transient refers to self-limiting and predictably resolving conditions or acute events (e.g., common cold or otitis media), reversible medical conditions that are successfully treated (e.g., resolved anemia), being unable to comply with study procedures due to administrative convenience (e.g., family issues or attending to a private matter), and/or being within the exclusion window for past medications and/or procedures, as outlined in [Section 5.2](#).

Subjects who failed any entry criteria for which no further treatment or spontaneous resolution is expected are not allowed to be rescreened. Daily OA knee pain diary noncompliance is not a transient event and subjects with knee pain diary noncompliance may not be rescreened.

Any rescreened subject must be reconsented and will be issued a new subject number. All screening procedures and assessments must be performed at rescreen; no results or data may be used from the previous screen. Target knee selection may not be changed at rescreen without the permission of the Medical Monitor.

5.5 STRATEGIES FOR RECRUITMENT AND RETENTION

A detailed recruitment and retention plan will be maintained by the Sponsor.

5.6 PARTICIPANT WITHDRAWAL OR TERMINATION

5.6.1 REASONS FOR WITHDRAWAL OR TERMINATION

Because the study treatment requires only one injection, best efforts will be made to encourage subjects to attend all follow-up visits. Subjects will be informed they are free to withdraw from the study at any time and for any reason. A premature discontinuation from the study will occur when a subject who signed informed consent ceases participation in this study, regardless of circumstances, prior to completion of the defined study period. Subjects can be prematurely discontinued from the study for one of the following reasons:

- AE
- Total or partial knee replacement of the target knee
- Lost to follow-up after a minimum of 3 attempts have been made to contact the subject, including sending a registered letter
- Withdrawal by subject for reason other than lack of efficacy
- Subject non-compliance
- Physician decision for reason other than lack of efficacy
- Study terminated by Sponsor
- Site terminated by Sponsor
- Request by regulatory authority
- Lack of efficacy
- Pregnancy
- Death
- Randomized by mistake without study treatment
- Other

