The WPI&SS assessment consists of a body map that determines a subject's areas of pain or tenderness (WPI) and symptom severity (SS) questions. The WPI&SS assessment used in this study is modified from that described in [\(Clauw 2014\)](#). A WPI&SS assessment will be

completed by the subject at the Screening Visit and Day 1.

Upon completion of the WPI&SS assessment, the subject will sign or initial the source document and date it to indicate that the assessment is reported accurately.

The WPI&SS assessment sheets will be provided by the Sponsor and may not be reproduced.

Electronic Diary Device Provision and Training

Detailed instructions and site training regarding subject electronic questionnaire completion will be provided to the investigational center. Electronic diary device provisioning to the subject will occur at the Screening Visit and electronic diary devices are to be returned to the site at Week 28 (EOS)/ET.

Subject training for electronic diary and questionnaire completion on the electronic diary device is required at the Screening Visit prior to subject completion of the pain NRS, WOMAC, and Patient Global Assessment questionnaires. Training will remain available on the electronic diary device throughout the study in case subject retraining is needed.

Additionally, at the Screening Visit, subjects will have training on accurate pain reporting and placebo response reduction prior to subject completion of the pain NRS, WOMAC, and Patient Global Assessment questionnaires. It is recommended that subjects complete the training on accurate pain reporting and placebo response reduction at Day 1 and Weeks 4, 12, and 24.

Pain Numeric Rating Scale

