7.3.6 EARLY TERMINATION VISIT

If possible, the following procedures and assessments should be performed within 14 days of subject premature withdrawal or termination.

- Collection of AE and concomitant procedures/therapies/medication data

Protocol SM04690-OA-10

Samumed, LLC

AM03V00

12 May 2020

- Review of medical history
- Assessment of NSAID/acetaminophen usage
- Physical examination, including knee examination of both knees
- Weight measurement
- Vital sign measurements (pulse rate, blood pressure, respiratory rate, and temperature)
- Venipuncture and collection of samples for clinical laboratory tests

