4.4.3 Prohibited Medications, Treatments, and Procedures

During the conduct of the study, certain medications, treatments, and procedures were prohibited (see Protocol Section 7.6). The overall intent of these prohibitions was to minimize any possible bias in the assessment of the clinical trial endpoints. However, the protocol did allow for the use of these prohibited therapies if and only if they were required to ensure subject safety.

Investigators were instructed to notify the sponsor's Medical Monitor, who would note the prohibited therapy as a protocol deviation. These deviations were categorized as major or minor depending on the nature and timing of the interventions. Subjects were not automatically discontinued based upon prohibited therapy use, allowing for continued data collection and assessment of the impact of prohibited therapy on key endpoint data.

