7.1.2 Mixed-Effects Model for Repeated Measures

A mixed-effects model for repeated measures (MMRM) will be used to evaluate Pain NRS, WOMAC, and Patient Global Assessment outcome measures. The null hypothesis is that the mean difference in the endpoints between the two treatment groups is zero, versus the alternative hypothesis that this difference is not zero. The hypotheses can be expressed as follows:

$$H_0: (\beta_1 - \beta_0)_t = 0$$

$$H_A: (\beta_1 - \beta_0)_t \neq 0,$$

where β_0 refers to the least squares mean change from baseline in the placebo group and β_1 refers to the least squares mean change from baseline in the active treatment group, evaluated at timepoint t .

For Pain NRS, the model will be estimated assuming a Toeplitz variance-covariance matrix. The Toeplitz structure is a more generalized form of autoregressive-1 (AR1) structure, allowing the data to inform how the correlation between within-subject observations decreases over time instead of implicitly defining a uniform decay structure (Kincaid, 2005).

For WOMAC and Patient Global Assessment, the model will be estimated assuming an unstructured variance-covariance matrix, allowing the data to fully inform the correlation between within-subject observations (Kincaid, 2005).

MMRM presumes that missing data are not caused by something observable within the conduct of the trial (i.e. missing-at-random [MAR]). It is plausible to presume a MAR mechanism as there have been no observed tolerability issues to the administration of study injection during the prior development trials. Additionally, the study injection cannot be removed after it has been administered, eliminating study drug discontinuation as a source of treatment estimate confounding.

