9.1 Estimands

The primary estimand for this trial is the difference between a single injection of SM04690 versus placebo in mean baseline-adjusted change in Pain NRS at Week 12, whether or not NSAIDs/acetaminophen are used (i.e. presuming a treatment policy of background NSAID and acetaminophen usage), and analyzed with MMRM, including all collected Pain NRS data in subjects in the FAS.

A summary of all estimands defined for this study is available in [Appendix 3](#).

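### Subjects can be taken out of a single-injection study for outcome-related reasons, and home diary collection ends with them, leaving avoidable gaps at Weeks 12 and 24 that the SAP's MAR argument does not address

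*Protocol*

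**What the plan says.** - **Protocol 5.6.1** begins with retention: "Because the study treatment requires only one injection, best efforts will be made to encourage subjects to attend all follow-up visits". It continues: "Subjects can be prematurely discontinued from the study for one of the following reasons". Fourteen reasons follow, among them AE, lack of efficacy, subject non-compliance and "Physician decision for reason other than lack of efficacy".
- **Protocol 5.6.2** asks for ET procedures, the date and the reason. It provides for no later outcome collection.
- **Protocol 7.3.6** on the ET visit: "If possible, the following procedures and assessments should be performed within 14 days of subject premature withdrawal or termination". The list covers AEs and concomitant therapy, medical history, NSAID/acetaminophen use, examinations, weight, vital signs and laboratory samples. Pain NRS, WOMAC and Patient Global Assessment are not on it.
- **Protocol 7.1.1**: "electronic diary devices are to be returned to the site at Week 28 (EOS)/ET".
- **SAP 7.1.2** gives two grounds for MAR. One is the absence of tolerability problems in earlier trials. The other is that an injection cannot be removed, "eliminating study drug discontinuation as a source of treatment estimate confounding".
- **SAP 9.1** defines the primary estimand by MMRM, "including all collected Pain NRS data in subjects in the FAS". Appendix 3 lists two intercurrent events, prohibited medication and NSAID/acetaminophen change. Study withdrawal is not listed.
- **SAP 4.4.3**, on prohibited therapy: "Subjects were not automatically discontinued based upon prohibited therapy use, allowing for continued data collection". Protocol 10.6.3 likewise keeps unblinded subjects in follow-up.
- **SAP 7.1.6, 7.1.6.1 and Appendix 3** plan multiple imputation (MI) under MAR and a tipping-point analysis for all six tested hypotheses.

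**The concern.** After Day 1 there is no treatment left to stop, so the usual distinction between stopping treatment and stopping follow-up matters more here. An AE, a lack of benefit or a physician's decision does not by itself prevent a willing subject from answering a pain question at home each evening. The protocol does not draw that distinction: leaving the study for one of these reasons also ends the diary.

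The SAP then argues for MAR from the absence of drug discontinuation. That is correct as far as it goes, but here the route to missing data is study discontinuation, on which the argument is silent. At stake are Week 12 and Week 24 values in subjects who may differ from those who stay. The MMRM fills these gaps implicitly from the remaining subjects. If the departing subjects' later pain differs from that prediction, and more so in one arm, the estimated treatment difference is off.

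**Working it through.** **1. The plan's own figures.** Inputs from Protocol 10.5 and SAP 5: difference 0.8, correlation 0.25, two-sided alpha 0.05, 10% dropout. Follow-up SD is 3.0 with 325 evaluable per arm, or 2.4 with 225 after re-estimation.

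SE = SD × √(1 − 0.25²) × √(2/n); power = Φ(0.8/SE − 1.96).

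- n = 325: SE = 3.0 × 0.968 × √(2/325) = 0.228; power 94.0% (plan: 93.5%).
- n = 225: SE = 2.4 × 0.968 × √(2/225) = 0.219; power 95.5% (plan: 94.3%).
- Randomized: 2 × ⌈325/0.9⌉ = 724 (Protocol about 726, SAP about 725); 2 × ⌈225/0.9⌉ = 500 (SAP about 500).

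The power figures agree within the noise of 1,000 simulations: √(0.943 × 0.057/1000) is about 0.7 percentage points.

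**2. How many subjects.** The planned dropout is 0.10 × 500 = 50, or 0.10 × 726 ≈ 73. This counts all reasons, so it bounds the number the change could reach if dropout is as planned. The documents give no split by reason or arm.

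**3. What is lost.** The device comes back at ET and the ET list has no tested outcome. The rule in SAP 7.1.5 that assigns ET assessments to a scheduled visit therefore recovers nothing for these endpoints. A subject leaving before Week 12 loses both key values; one leaving between Weeks 12 and 24 loses only the later.

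**4. Possible size.** Let d be the fraction missing in an arm and k the number of NRS points by which the missing values are worse than MAR predicts. Differences are active minus placebo. Then

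effect with everyone followed = MMRM estimate + (d_active × k_active − d_placebo × k_placebo).

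All d and k below are assumptions, and the MMRM estimate is set to −0.80.

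| Missing, active/placebo | k, active/placebo | Shift | Effect with everyone followed |
|---|---|---|---|
| 10%/10% | equal | 0 | −0.80 |
| active higher by 2 to 5 points | 1 to 2 in both | 0.02 to 0.10 | −0.78 to −0.70 |
| 12%/8% | 1 to 3 in both | 0.04 to 0.12 | −0.76 to −0.68 |
| 8%/12% | 1 to 3 in both | −0.04 to −0.12 | −0.84 to −0.92 |
| 10%/10% | 1, 2, 3/0 | 0.10, 0.20, 0.30 | −0.70, −0.60, −0.50 |

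The second row is 0.02 × 1 = 0.02 up to 0.05 × 2 = 0.10, or 2.5% to 12.5% of 0.8. The last row reaches 0.10 × 3 = 0.30, or 37.5%. The sign depends on which arm loses more.

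**5. Does outcome-related withdrawal break MAR?** This was simulated with a true effect of −0.80, SD 2.4, an assumed correlation of 0.7 between an earlier and the final pain value, 2,000 per arm and 600 runs. Withdrawal rose with pain under the same rule in both arms, giving about 12% missing on placebo and 9% on active. Simulation error is about 2.4 × √(2/2000)/√600 = 0.003.

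| Withdrawal driven by | MMRM-type estimate | Estimate ignoring post-baseline pain |
|---|---|---|
| pain already recorded | −0.80 | −0.75 |
| pain not recorded | −0.76 | −0.73 |

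The MMRM is unbiased in the first case and off by about 0.04 in the second. The right-hand column resembles the SAP's MI, which uses baseline only and treats each timepoint separately.

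**6. Against the planned precision.** A bias of 0.10 is under half of the SE of 0.219; 0.30 is about 1.4 SEs. With an observed −0.80 and 10% missing, the active-arm shift needed to lose significance is (0.8 − 1.96 × 0.219)/0.10 ≈ 3.7 points. So at the planned effect even the 3-point case changes the size of the estimate but not its significance.

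**The case against.** A reader might infer four stronger things, none of which the documents support.

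- *That the plan ignores departures from MAR.* It does not. MI and a tipping-point analysis are planned for every tested hypothesis. They have limits: the tipping point runs only after a significant MI result and describes shifting only the treatment group. They also test the assumption without recovering any data. But the check exists.
- *That withdrawal for lack of efficacy breaks MAR.* Pain is recorded daily up to withdrawal and SAP 9.2.1 uses all timepoints. If withdrawal depends only on that record, the MMRM is unbiased.
- *That the treatment-policy estimand promises follow-up after withdrawal.* In Appendix 3 that strategy is attached only to prohibited medication and NSAID/acetaminophen change.
- *That 5.6.1 orders removal.* The wording is permissive, and the list includes death, loss to follow-up and a catch-all, so it serves partly as disposition codes. Physician decision expressly excludes lack of efficacy. Some subjects coded as lack of efficacy will have chosen to leave and may decline further entries.

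The plan also works to limit loss: best-efforts retention, free use of NSAIDs/acetaminophen, diary surveillance with site follow-up, and continued follow-up of unblinded subjects and prohibited-therapy users.

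Finally, the SAP is written in the past tense and was signed in October 2021. If collection has closed, the data part of the fix comes too late for this trial and only the SAP part remains.

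All of this stands. What it leaves untouched is that no text lets a willing subject who leaves for one of these reasons keep the diary going, and that SAP 7.1.2 does not mention study withdrawal.

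**Conclusion.** The point holds as a cheap improvement, not as a defect that invalidates the primary analysis. The documents establish that outcome collection ends with study discontinuation, that nothing about the treatment or the remote endpoints requires this, and that the MAR justification covers only tolerability and drug discontinuation.

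They do not establish that bias will occur, or its direction. It is nil if missing fractions and departures from MAR are the same in both arms. It is 0.02 to 0.10 NRS points if the arms differ by 2 to 5 percentage points in such missingness with a departure of 1 to 2 points. It reaches about 0.3 points if 10% of active-arm values are missing and 3 points worse than MAR predicts while placebo follows MAR. These rest on assumed rates and departures. The most secure gain is simply fewer missing Week 12 and Week 24 values.

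**What to change.** - **Protocol 5.6.1 and 5.6.2**: state that AE, lack of efficacy, non-compliance and physician decision are recorded as reasons but do not by themselves end remote diary and questionnaire collection. Subjects who agree keep the device and continue through Week 12 and then Week 24, unless they withdraw consent for this, die, are lost to follow-up, or the site or study closes.
- **Protocol 7.1.1**: bring the device-return text into line. Consent wording follows.
- **SAP 9.2.1 and 9.3.1**: confirm that these entries enter the FAS MMRM. The estimand in SAP 9.1 already takes in all collected pain data, so little changes.
- **SAP 7.1.2**: address study withdrawal in the MAR justification, saying why withdrawal is expected to depend on recorded rather than unrecorded pain.

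The cost is wording, some devices returned later, and reminders to at most about 50 (of 500) or 73 (of 726) subjects at the planned dropout. No visit, procedure or treatment is added. Uptake will probably be partial, since some subjects will decline further entries.
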